7.1 Study Medication Exposure and Treatment Compliance

7.1.1 *Extent of Exposure*

In Part A, the single dose of LY or placebo will be administered at the clinical research unit (CRU) under the supervision of the investigator. As a result, subject compliance will be ensured. A by-subject listing of the treatment received by each subject for each dosing period in Part A will be provided.

In Part B, the daily dose of LY or placebo will be administered at the CRU on Days 1, 2, 7, 14, 21, 28, and 29, while doses on the intermittent days will be administered by the subject while at home. Each subject will document in a daily diary the administration of each daily dose along with the time of dosing and the time of the first meal of the day. From the daily diaries and the Medication Dosing pages of the CRF, the total number of doses received and date of last dose of study medication can be determined. The extent of exposure can be derived as:

$$\text{Extent of Exposure} = \text{Date of last dose of study drug} - \text{Date of 1}^{\text{st}} \text{ dose of study drug} + 1.$$

Extent of exposure will be reported as a continuous variable by treatment group. In addition, extent of exposure will be reported as a categorical variable using the categories: 1 to <7 days, 7 to <14 days, 14 to <21 days, 21 to <29 days, and 29 days.

7.1.2 Treatment Compliance

Compliance for the study will be derived as:

$$\text{Compliance} = \text{Total number of doses received} / \text{Extent of Exposure}.$$

Each subject in Part B is supposed to take $\geq 80\%$ of the intended dose to be deemed compliant with study drug administration. Compliance with study medication will be reported by treatment group using the categories: < 80% compliance, 80% to < 100% compliances, and 100% or greater compliance.

A by-subject listing of each subject's daily dose will be provided for the subjects in Part B.

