8.5. Treatment Compliance

In Part A, LY3202328 or placebo will be administered at the CRU under the supervision of the investigator. As a result, subject compliance will be ensured.

In Part B, simvastatin and atorvastatin will be administered at the CRU under the supervision of the investigator. As a result, subject compliance will be ensured. LY3202328 or placebo will be administered at the CRU (on days of confinement) and subjects will also self-administer LY3202328 at home between study visits. Compliance will be assessed by subject diary entries, direct questioning, and enumeration of returned capsules.

Subjects who are significantly noncompliant in Part B will be discontinued from the study. The subject must take $\geq 80\%$ of the intended dose to be deemed compliant with study drug administration. Similarly, a subject will be considered significantly noncompliant if he or she is judged by the investigator to have intentionally or repeatedly taken more than the prescribed amount of medication ($\geq 120\%$ of the intended dose taken in a visit interval).

Study medication administration data and deviation(s) from the prescribed dosage regimen should be recorded in the subject's CRF.

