11.2.3. Treatment Compliance

Compliance will be ensured for administration of LY3202328 in Part A and administration of LY3202328, simvastatin and atorvastatin in Part B, as study drug will be administered at the CRU under the supervision of the investigator.

Treatment compliance for LY3202328 in Part B will be ensured on days of subject confinement to the CRU and study visits, but will be assessed by comparing returned pills with dispensed pills (the percentage of the actual number of capsules taken versus the number of capsules expected to be taken) for dosing days while not confined to the CRU.

Subjects who demonstrated significant noncompliance (<80% or >120% of the intended dose taken in a visit interval) will also be summarized.

Study medication administration data and deviation(s) from the prescribed dosage regimen should be recorded in the subject's CRF.

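### SAP 7.1.2 does not produce the visit-interval compliance summary promised in Protocol 11.2.3, and its table puts over-use in the same cell as perfect compliance

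*SAP*

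**What the plan says.** Protocol 11.2.3 assesses Part B home dosing by comparing returned with dispensed medication, that is, "the percentage of the actual number of capsules taken versus the number of capsules expected to be taken". It then commits to a specific output: "Subjects who demonstrated significant noncompliance (<80% or >120% of the intended dose taken in a visit interval) will also be summarized". Protocol 8.5 names diaries, questioning and counts of returned capsules as the sources. It sets 80% of the intended dose as the lower limit and treats over-use within a visit interval as significant non-compliance. There the upper limit is at or above 120%; in 11.2.3 it is above 120%.

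SAP 7.1.1 takes the number of doses and the last dose date from the diaries and the dosing pages of the CRF. It defines extent of exposure as last dose date minus first dose date plus 1. SAP 7.1.2 divides the number of doses by that extent, giving one figure per subject for the whole study. It repeats the 80% requirement and reports three categories: below 80%, "80% to < 100% compliances, and 100% or greater compliance". The section closes with a further output: "A by-subject listing of each subject's daily dose will be provided for the subjects in Part B". It does not mention visit intervals, capsule counts or an upper limit, and it does not say that it departs from the protocol.

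**The concern.** The two documents measure different things. The protocol looks within each interval, in capsules, with limits on both sides. The SAP looks across the whole study, in doses per elapsed day, with a limit only on the low side. A programmer who follows the SAP will produce a table in which over-use of any size cannot be told from exact adherence, and in which a missed home interval can be diluted by adherence elsewhere.

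By SAP 7.1.1, 22 of the 29 Part B doses are taken at home, in a first-in-human study reported by assigned dose. The compliance table is the planned summary of whether that dose was taken. With 8 active subjects per cohort, one misclassified subject is 1/8 = 12.5% of a dose group.

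**Working it through.** **Inputs.** Dosing is once daily for 29 days (Protocol 6.1.2). Clinic doses are on Days 1, 2, 7, 14, 21, 28 and 29, so 7 clinic and 29 − 7 = 22 home doses (SAP 7.1.1). Capsule strengths are 1, 5 and 50 mg (Protocol 8.1.1). Part B doses are 5, 20, 100 and 300 mg (Protocol Table GSEA.2).

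**Assumption.** The documents do not define a visit interval. I take the home blocks Days 3–6 (4 doses), 8–13 (6), 15–20 (6) and 22–27 (6), which total 22. The dosing patterns are illustrations, not data.

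**Reproducing the plan's figure.** Extent for a completer = 29 − 1 + 1 = 29 days, which matches the planned duration and the SAP's top exposure category.

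**Comparison.** SAP ratio = doses received / 29. Protocol ratio = taken / expected within the interval. When whole doses are missed or added, the capsule ratio equals the dose ratio.

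| Pattern | SAP ratio | SAP cell | Interval ratio | Protocol 11.2.3 |
|---|---|---|---|---|
| No deviation | 29/29 = 100% | 100% or more | 100% throughout | within limits |
| Miss all 4 on Days 3–6 | 25/29 = 86.2% | 80 to <100% | 0/4 = 0% | below 80% |
| Miss 5 of 6 on Days 8–13 | 24/29 = 82.8% | 80 to <100% | 1/6 = 16.7% | below 80% |
| Double the 4 on Days 3–6 | 33/29 = 113.8% | 100% or more | 8/4 = 200% | above 120% |
| Double the 6 on Days 8–13 | 35/29 = 120.7% | 100% or more | 12/6 = 200% | above 120% |
| Double all 22 home doses | 51/29 = 175.9% | 100% or more | 200% throughout | above 120% |
| Miss 3 on Days 8–13, add 3 on Days 15–20 | 29/29 = 100% | 100% or more | 3/6 = 50%; 9/6 = 150% | both outside |

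Six missed doses are needed before the SAP ratio falls below 80% (24/29 = 82.8%; 23/29 = 79.3%). A fully missed four-day block alone therefore never does so; a fully missed six-day block does.

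**Sensitivity to the interval.** If the Day 7 clinic dose is included, the missed block is 1/5 = 20% and the doubled block 9/5 = 180%. Protocol 8.1 lists Day 3 as a clinic dosing day. On that reading the home block is Days 4–6: missing it gives 26/29 = 89.7% against 0/3 = 0%, and doubling it gives 32/29 = 110.3% against 6/3 = 200%. The conclusion is the same each time.

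**Would a whole-study category above 120% be enough?** No. It needs at least 35 doses (34/29 = 117.2%; 35/29 = 120.7%), so doubling the four-day block (33/29) would still not be flagged.

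**Partial doses.** The largest capsule that fits gives 4 × 5 mg, 2 × 50 mg and 6 × 50 mg for 20, 100 and 300 mg, so these doses need several capsules. Half the capsules at every home dose is 50% per interval and (7 + 22 × 0.5)/29 = 18/29 = 62.1% of all capsules. The SAP ratio is 29/29 = 100% if a partly taken dose counts as one, and 7/29 = 24.1% if it counts as none. The SAP does not say which.

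**The case against.** The strongest reply is that the SAP as a whole does not conceal dosing. The daily-dose listing sits in the same section, and 40 planned subjects can be read by eye. Protocol 8.5 has dosing deviations recorded in the CRF. SAP 3.1 tabulates protocol violations for Part B, and SAP 3.2 tabulates reasons for discontinuation. This stands in part: a reader might infer that the SAP hides overdosing, and that goes too far. But a listing is not the summary promised in Protocol 11.2.3, and SAP 3.1 does not name non-compliance.

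Three further inferences are tempting and not supported.

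- *Early stopping is masked because the denominator ends at the last dose.* The exposure categories in SAP 7.1.1 and the disposition table in SAP 3.2 show early stopping, and compliance while on treatment is a legitimate measure.
- *Misclassified subjects should have been discontinued.* For over-use, Protocol 8.5 requires the investigator to judge it intentional or repeated, and its 80% limit names no visit interval. Discontinuation is also decided during conduct, not from a final table.
- *By-dose safety, PK or lipid results would change.* No analysis population or model in the documents uses the compliance category, Day 28 and 29 doses are supervised, and drug concentrations are measured directly.

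It can also be said that Protocol 6.1.2 dispenses doses to last until the next visit and mentions no surplus, so doubling every home dose may be impracticable. That is fair for the extreme example. Still, the protocol sets a 120% limit, so it treats over-use as possible. Finally, the difference between the two 120% limits affects only a value of exactly 120%.

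**Conclusion.** The concern holds as a gap between protocol and SAP in compliance reporting. The summary promised in Protocol 11.2.3 cannot be produced from SAP 7.1.2, and the planned table misplaces subjects: 86% for an interval at 0% (20% with the Day 7 dose), and 114% to 176% in the same cell as 100%. The first result depends on how the visit interval is drawn, but every reading tested breaches the protocol limits. The second does not depend on it, because the top category is open-ended.

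The partial-dose point is conditional: it applies to 20, 100 and 300 mg, and only if a partly taken dose counts as one. Overall under-dosing through six or more missed days is still shown. The consequence is a compliance table that cannot support a statement about over-use or interval adherence; it is not a bias in the safety, PK or lipid analyses.

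**What to change.** In SAP 7.1.2:

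- Add compliance per visit interval, as capsules taken (dispensed minus returned) divided by capsules expected, with categories below 80%, 80 to 120% and above 120%, by treatment group.
- Define the visit interval, including whether the clinic dose that closes it is counted and how Day 3 is treated.
- State how a partly taken multi-capsule dose enters the count of doses received.
- Keep the whole-study ratio as a supplement, and keep the daily-dose listing.

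Reconcile the upper limit between Protocol 8.5 (at or above 120%) and 11.2.3 (above 120%), and assign a value of exactly 120% accordingly.

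The cost is SAP wording, minor programming and a longer table. The protocol already calls for diaries, returned containers and capsule counts, so no new data are needed.

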7.2 Adverse Events

Investigators will monitor the safety of subjects and will be responsible for their medical care during the study. The investigator will interpret and document adverse events and will indicate whether each event is serious and the strength of causality to the study medication. The subject will be followed until adverse events are resolved.

Only those adverse events (AE) that emerge or worsen after the date of first dose of study medication, i.e. treatment emergent adverse events (TEAE), will be summarized. Adverse events with a missing start date will also be classified as TEAE.

Summaries of TEAE will include the number of subjects with at least one TEAE for each treatment group. When reporting by system organ class (SOC) and preferred term (PT), the reports will present the SOC in alphabetical order; while PTs within the SOC will be presented in order of overall decreasing frequency of occurrence in the combined LY treatment groups. A subject with multiple TEAEs (different PTs) coded to the same SOC will be counted only once for that SOC, but will be counted each time for different PTs within that SOC. A subject with separate events of the same PT (different start/stop dates) will be counted only once in the frequency tables for that PT.

In Part A, TEAEs will be reported using the treatment that the subject most recently received. Adverse events that occur on the first day of a dosing period will be assigned to the treatment received on that day.

No statistical testing will be performed for comparisons of TEAEs.

An overview of all TEAEs for both Parts A and B will also be provided by treatment group using the types of TEAEs defined in the following subsections.

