11.3.1. Safety Analyses

11.3.1.1. Clinical Evaluation of Safety

All LY3202328 and protocol procedure AEs will be listed, and, if the frequency of events allows, safety data will be summarized using descriptive methodology.

The incidence of symptoms for each treatment will be presented by severity and by association with investigational product as perceived by the investigator. Symptoms reported to occur prior to study entry will be distinguished from those reported as new or increased in severity during the study. Each symptom will be classified by the most suitable term from the current medical regulatory dictionary. Severity of the AE will be assessed according to the "Toxicity Grading Scale for Healthy Adult and Adolescent Volunteers Enrolled in Preventive Vaccine Clinical Trials 2007".

The number of investigational product-related SAEs will be reported.

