11.3.1.2. Statistical Evaluation of Safety

The primary endpoint of this study is the number and severity of treatment-emergent adverse events (TEAEs), clinical laboratory abnormalities, changes in vital sign measurements, and other safety endpoints after administration of LY3202328 or placebo. Summary statistics will be provided by dose group and for all study subjects combined wherever appropriate. For

continuous variables, summary statistics will include number of subjects, mean, median, SD, minimum, and maximum. Categorical endpoints will be summarized using number of subjects, frequency, and percentages. Additional analysis will be performed if warranted upon review of the data.

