SAD	single ascending dose(s)
screen	The act of determining if an individual meets minimum requirements to become part of a pool of potential candidates for participation in a clinical trial.
SD	standard deviation

SUSAR	suspected unexpected serious adverse reaction
t_{1/2}	half-life
TC	total cholesterol
TEAE	treatment-emergent adverse event: Any untoward medical occurrence that emerges during a defined treatment period, having been absent pretreatment, or worsens relative to the pretreatment state, and does not necessarily have to have a causal relationship with this treatment
T_{max}	time to reach maximum plasma concentration
TG	triglyceride(s)
TSH	thyroid stimulating hormone
ULN	upper limit of normal
V/F	apparent volume of distribution

**Appendix 2. Schedule of Events for Protocol
I8Q-MC-GSEA**

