7.2.2 Serious Treatment-Emergent Adverse Events

A serious TEAE (SAE) is a TEAE that met one or more of the following criteria:

- Is fatal
- Is life-threatening
- Requires or prolongs hospitalization
- Is significantly or permanently disabling or incapacitating
- Constitutes a congenital anomaly or a birth defect or
- Jeopardizes the subject and may require medical or surgical intervention to prevent one of the above outcomes

For both Parts A and B, SAEs will be summarized for each treatment arm by SOC and PT for the Safety population. These reports will also include the total number of SAE for each SOC and PT. A listing of all SAE will also be provided. The listing will include the criteria that a TEAE met to be declared an SAE.

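### SAP 7.2 counts adverse events as treatment-emergent only after the date of first dose, which as written omits first-dose-day onsets in Part B and contradicts the Part A first-day rule

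*SAP*

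**What the plan says.** SAP 7.2 summarises "Only those adverse events (AE) that emerge or worsen after the date of first dose of study medication" and calls these TEAEs. Three other statements in the SAP bear on the same boundary.

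- Also in SAP 7.2, for undated events: "Adverse events with a missing start date will also be classified as TEAE".
- Also in SAP 7.2, in the paragraph on Part A: "Adverse events that occur on the first day of a dosing period will be assigned to the treatment received on that day". Part B has no equivalent.
- SAP 5 sets the boundary for concomitant medications at on or after the date of the first dose of LY or placebo.

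Protocol Appendix 1 defines a TEAE as "Any untoward medical occurrence that emerges during a defined treatment period, having been absent pretreatment, or worsens relative to the pretreatment state". It does not mention excluding the dosing date.

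TEAEs are part of the primary endpoint in Protocol 11.3.1.2: "The primary endpoint of this study is the number and severity of treatment-emergent adverse events (TEAEs), clinical laboratory abnormalities, changes in vital sign measurements", together with other safety endpoints. Further SAP tables start from the TEAE set. For serious events, SAP 7.2.2 says "A serious TEAE (SAE) is a TEAE that met one or more of the following criteria". The related, maximal-severity and common non-serious tables (SAP 7.2.5 to 7.2.7) are also subsets or breakdowns of TEAEs.

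**The concern.** A programmer who follows the sentence would flag an event only if its start date is later than the first-dose date. An event that begins two hours after the first capsule shares its date with that dose and fails the test.

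The result is odd beside the neighbouring rules. An event with no start date is kept, while one documented as starting on Day 1 is lost. A drug given on Day 1 to treat such an event is summarised as a concomitant medication under SAP 5, but the event itself is not summarised.

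The omitted day matters. Dosing is in the morning, and preclinical time to peak is 1 to 3 hours in most species (Protocol 4.2), so the first peak concentration should fall on the first-dose date. With 8 LY subjects per Part B dose level, a single missing event visibly changes a table.

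**Working it through.** The documents give no figure on this point, so there is nothing to reproduce. The check counts the dosing days affected and then illustrates what could be lost.

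**1. Part A.** The inputs are the sequences in Figure GSEA.1, with three subjects per sequence. The last column counts administrations that fall on a subject's first-dose date.

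| Treatment | Planned administrations | On first-dose date |
|---|---|---|
| 1 mg | 6 | 6 |
| 3 mg | 6 | 6 |
| 10, 30, 100, 300 mg fasted | 4 × 6 = 24 | 0 |
| 30 mg fed | 6 | 0 |
| Placebo fasted | 18 | 6 |
| Placebo fed | 3 | 0 |
| Total | 63 | 18 |

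The 63 is 54 in Periods 1 to 3 (18 subjects × 3) plus 9 in the fed period; the optional 600 mg dose is left out. Day 1 of every later period is already after the subject's first-dose date, so it counts under either reading. The exceptions would be a replacement subject who enters in a later period, or a separate new 600 mg cohort.

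**2. Part B.** Four cohorts of 8 LY and 2 placebo (Protocol 6.1.2) give 4 × 8 = 32 LY and 4 × 2 = 8 placebo, 40 in all. Each subject has one first-dose date among 29 dosing days: 1/29 = 3.4% of dosing days, at every dose level.

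**3. How much of the first dose falls on that date.** Inputs: projected human half-life of 6 to 8 hours (Protocol 4.2), and an assumed 14 to 18 hours from a morning dose to midnight. As a rough guide that ignores absorption time, the share eliminated is 1 − 2^(−h/t½).

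- Lowest: 1 − 2^(−14/8) = 70%.
- Highest: 1 − 2^(−18/6) = 87.5%, about 88%.

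**4. Chance that at least one event is omitted per Part B dose level.** With 8 LY subjects this is 1 − (1 − p)^8, where p is the chance that a subject has a Day 1 onset. The documents give no value for p, so these are assumed values.

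| p | Chance of at least one |
|---|---|
| 5% | 34% |
| 10% | 57% |
| 20% | 83% |
| 30% | 94% |

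**5. Side by side.** In Part A, the first-day sentence assigns a treatment to events on the day of dosing and does not exempt Period 1. That has little purpose if Period 1 events of that day are then discarded, so for Period 1 the two sentences conflict. In Part B only the date rule applies.

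**The case against.** The strongest reply is that this is loose wording and that the intent is inclusive. The Part A first-day sentence and the rule for undated events both point that way, and a sensible programmer might use on or after regardless. For Part A this largely stands: the better reading is that first-day events are meant to be reported, and what remains is a contradiction confined to a subject's first dosing day. For Part B it does not stand, because nothing there overrides the stated rule.

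A second reply is that study medication is not defined in SAP 7.2. If it included the statin given on Day -7, Part B Day 1 events would count. SAP 7.1.1 uses the term for LY or placebo, so this is a weak rescue. It would also turn events before any LY or placebo dose into TEAEs.

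Three limits are fair. Protocol 11.3.1.1 still says "All LY3202328 and protocol procedure AEs will be listed". An event that starts on Day 1 and worsens later still qualifies. Dose escalation rests on review of the safety data (Protocol 8.3.1), not on these tables.

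A reader might go further and infer three things that the documents do not support.

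- That every Day 1 is lost from the primary endpoint. Later Part A periods, including all planned 10 to 300 mg doses, are unaffected, and TEAEs are only one component of that endpoint.
- That the loss falls mainly on LY and so biases the comparison. The rule treats placebo alike, and the larger LY count simply reflects allocation.
- That the SAP flatly contradicts the protocol definition. Appendix 1 does not say when the treatment period begins, so the literal rule fits it poorly but is not an express contradiction.

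**Conclusion.** The point holds as a defect in a stated rule. Followed as written, SAP 7.2 removes first-dose-date onsets from the TEAE tables and those derived from them. In Part B that is one day for each of 40 subjects, with no text to restore the events. In Part A it is an internal contradiction over 18 of 63 planned administrations, at 1 mg, 3 mg and Period 1 placebo only.

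The day counts assume that planned enrolment and sequences are followed and that study medication means LY or placebo. The 70% to 88% and 34% to 94% figures are illustrations that rest on the assumed hours to midnight and the assumed event rates. No program specification is in the documents, so actual loss of events is a risk created by the wording, not something shown to have occurred. Laboratory, vital sign and ECG summaries and the general AE listing are untouched.

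**What to change.** Replace the sentence in SAP 7.2 with a definition on these lines: a TEAE is an AE that starts or worsens on or after the date of the first dose of LY or placebo. An event that starts on that date is left out only where a recorded onset time shows that it began before the dose and it did not worsen afterwards. A same-date event with no recorded time counts as a TEAE. State that this applies to Part A and Part B.

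This matches the boundary already used in SAP 5, names the anchor dose so that the Day -7 statin cannot be mistaken for it, and removes the conflict with the Part A first-day sentence. It does not depend on AE onset times, which the documents do not say are collected.

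The cost is one sentence and the matching program condition. A few events that began before dosing on the same day, with no time recorded, may be counted as TEAEs.
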